10 SUBJECT SELECTION

10.1 Inclusion Criteria

- 1) Males and females who have given written informed consent
- 2) Subjects must be at least 18 years of age or older
- 3) Subjects must weigh at least 40 kg
- 4) Good physical health as determined by a physical examination, an electrocardiogram (ECG) within normal limits, and laboratory screening tests within acceptable parameters (see exclusion criteria below)
- 5) DSM-5 diagnosis of mild to severe alcohol use disorder
- 6) Record an expired CO level of ≥ 10 ppm or a urinary cotinine level of ≥ 3 at screening and prior to randomization
- 7) Smoking an average of ≥ 5 cigarettes/day in the 30 days prior to randomization
- 8) Currently drinking at least 8 standard drink units (SDUs) per week in the 30 days prior to randomization for women and at least 15 SDUs per week in the 30 days prior to randomization for men
- 9) Subjects must provide evidence of stable residence in the last month prior to enrollment in the study, and have no plans to move in the next 9 months. Stable residence is a domicile in which an individual can operate as if it were his or her own homestead and does not include shelters or halfway houses
- 10) The pregnancy test for females of child-bearing potential at screen and prior to randomization must be negative. Additionally, women of child-bearing potential must be using an acceptable form of contraception. These include, but are not limited to: oral contraceptives, hormonal (levonorgestrel) or surgical implants, or barrier plus spermicide
- 11) Literate in English and able to read, understand, and complete the rating scales and questionnaires accurately, follow instructions, and make use of the behavioral treatments
- 15) Willing to participate in a treatment program for nicotine and alcohol dependence

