Analog Scale, Nicotine Craving Visual Analog Scale, CIWA-AR, Wisconsin Smoking Withdrawal Scale, and CES-D. In addition the PANAS assessment will be administered at Week 1, 3, 5, 7, 9 and 19 and the MOS-Sleep assessment will be administered at Week 1, 5, 9, 12, 16 and 19. The DrInC will be administered at Week 1, 4, 6, 9, 12 and 19.

CO levels will be measured at each visit during the study.

Salivary cotinine level is obtained before randomization and also at visit 15. In addition, in the event that a subject is unable to attend visit 15, they may be asked to provide a cotinine sample, via mail, which will be used to verify abstinence. In such a case, a saliva collection kit and instructions will be mailed to the subject with a prepaid return address envelope.

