14.26 Salivary Cotinine Level

Cotinine is the primary metabolite of nicotine and has a half-life of about 19 hours.[68] Salivary cotinine level will be used as an additional objective measure of tobacco exposure for those who are still smoking. We propose the use of 15 ng/ml of saliva cotinine as a cut-off level to segregate non-smokers (≤ 15 ng/ml) from smokers (> 15 ng/ml). The SRNT Subcommittee on Biochemical Verification[69] and Seccareccia et al.[70] both recommend that a cut-off level of cotinine (15 ng/ml) be utilized for saliva, serum, or plasma samples.

Each site will collect saliva samples on all subjects before randomization and at visit 15. In the event that a subject is unable to attend visit 15, they may be asked to provide a cotinine sample, via mail, which will be used to verify abstinence. In such a case, a saliva collection kit and instructions will be mailed to the subject with a prepaid return address envelope.

Samples will be sent to a specialty lab where cotinine analysis will be performed on those who report abstinence. All sites will use the same saliva cotinine collection kits to maintain uniformity across the study.

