older), gender, weight, and baseline smoking level will be considered as potential covariates for inclusion in the final analytic model.

If the saliva cotinine level satisfactorily achieves criteria for normality as longitudinal data, we will compare the groups using a mixed-effects linear model, accounting for a three-group design as well as the repeated measure of weeks (when appropriate). Otherwise, salivary cotinine level will be dichotomized as negative if ≤ 15 ng/ml and positive if > 15 ng/ml and analyzed using the generalized linear mixed models.

Logistic regression analysis will be used to compare point prevalence abstinence rates for the topiramate vs. placebo groups. We will determine point prevalence abstinence rates by a report of not smoking (0 cigarettes/day) for the entire period prior to a particular visit and an expiratory CO of < 10 ppm at the present visit.

[figure not shown]

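### The exploratory saliva cotinine models compare arms within a group selected by self-reported abstinence, because the only assay rule covers those who report abstinence

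*Combined protocol and SAP*

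**What the plan says.** Collection is universal. Section 14.26 states: "Each site will collect saliva samples on all subjects before randomization and at visit 15". Section 13.4 gives the same two time points, and Table 1 marks saliva cotinine at screening and at visit 15 (week 19 or early termination).

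Assay is not universal. Section 14.26 continues: "Samples will be sent to a specialty lab where cotinine analysis will be performed on those who report abstinence". No other assay rule appears in the documents. The same section introduces the measure as "an additional objective measure of tobacco exposure for those who are still smoking", which is the group that the assay rule leaves out.

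The analysis is in section 15.4, under the exploratory models: "If the saliva cotinine level satisfactorily achieves criteria for normality as longitudinal data, we will compare the groups using a mixed-effects linear model". That model has three groups and, where appropriate, week as a repeated measure. If normality fails, cotinine is split at 15 ng/ml and analysed with generalized linear mixed models. Section 15.4 also commits to analysing all randomized subjects by intention to treat. Nothing limits the cotinine models to self-reported abstainers or says how unassayed samples are handled.

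Eligibility in section 10.1 includes: "Smoking an average of ≥ 5 cigarettes/day in the 30 days prior to randomization".

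**The concern.** The models need cotinine values from all three randomized groups over time. The assay rule supplies values only for people whose self-report already says that they have quit. Quitting is what treatment is meant to change, so membership of the assayed group is itself an outcome and is expected to differ by arm.

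A comparison inside that group asks whether claimed quitters on one arm have lower cotinine than claimed quitters on another. The question of interest is whether treatment lowered tobacco exposure among those randomized. The first comparison can show no difference when treatment works, or a difference driven by how many smokers misreport relative to how many truly quit. The 15 ng/ml fallback uses the same samples and has the same fault.

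**Working it through.** **Which values exist**

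- *Literal reading of the assay rule.* Everyone is a smoker at entry (section 10.1), so nobody reports abstinence when the first sample is taken and no baseline is assayed. Each person has at most one value, at visit 15, so there is no repeated measure.
- *Wider reading.* The rule names people rather than time points. The stored baselines of those who later report abstinence might therefore also be assayed. Baselines would then exist, but only for the same selected people.
- *Common to both.* No self-reported smoker has a visit-15 value. A mixed model cannot recover those values under its usual missing-data assumptions, because no visit-15 value from that group is available to inform them.

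**Inputs**

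- Abstinence rates p of 10% and 28%, with 98 per arm (section 15.5). Alpha 0.017 and power 0.80 are from the same section.
- False-claim share f among smokers: not in the documents. Assumed 5%, with a range of 2% to 10%, equal in both arms.
- Cotinine is assumed to classify correctly: true abstainers at or below 15 ng/ml, smokers above it.
- Dropout is ignored.

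**The plan's own figure.** A two-sided pooled comparison of 10% with 28%, without continuity correction, gives 98 per arm at alpha 0.017 (99 at exactly 0.05/3); power at 98 is 0.802. The 98 reproduces and is used here only to size the assayed group.

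**Number assayed at visit 15** = 98 × [p + (1 − p)f]

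- f = 0: 98 × 0.10 = 9.8 and 98 × 0.28 = 27.4.
- f = 5%: 98 × (0.10 + 0.90 × 0.05) = 98 × 0.145 = 14.2, and 98 × (0.28 + 0.72 × 0.05) = 98 × 0.316 = 31.0.

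**Cotinine-positive share among those assayed** = (1 − p)f / [p + (1 − p)f]

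| f | p = 10% | p = 28% |
|---|---|---|
| 0 | 0% | 0% |
| 2% | 0.018/0.118 = 15.3% | 0.0144/0.2944 = 4.9% |
| 5% | 0.045/0.145 = 31.0% | 0.036/0.316 = 11.4% |
| 10% | 0.090/0.190 = 47.4% | 0.072/0.352 = 20.5% |

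**If everyone were assayed**, the positive share is 1 − p: 90% and 72%, whatever the value of f.

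The ratio of positive shares between arms is 90/72 = 1.25 in all randomized. Among those assayed it is 15.3/4.9 = 3.1, 31.0/11.4 = 2.7 and 47.4/20.5 = 2.3 as f rises from 2% to 10%. With no false claims the assayed groups do not differ at all, although the true quit rates are 10% and 28%.

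**The case against.** The strongest reply is that the documents do not clearly restrict the assay. Section 14.26 does not say that only self-reported abstainers are assayed, section 13.4 says "Salivary cotinine level is obtained before randomization and also at visit 15", and the stated purpose and the longitudinal model both suggest wider testing. One narrow sentence stands against several broader ones.

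Part of this stands. A reader might infer that no baseline value can exist and that the mixed model cannot be fitted at all. The documents do not support that as a categorical claim: it holds on the literal reading, but the text does not exclude assaying stored baselines of later abstainers. The selection at visit 15 survives both readings. If wider testing was intended, the assay sentence has to change.

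A reader might also infer that the trial's smoking result is compromised. It is not. The primary smoking outcome rests on self-report and carbon monoxide (section 15.3), the cotinine model is exploratory, and saliva cotinine is not named in the outcome lists of section 15.1.

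It can also be said that section 15.4 hedges on normality and on the repeated measure, and already plans the 15 ng/ml split. That is true, but neither hedge changes who has a value.

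Finally, the counts are only indicative. The 10% and 28% are continuous-abstinence rates taken from a bupropion trial, the share reporting abstinence at visit 15 may differ, and the abstract expects 30% dropout.

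**Conclusion.** The point holds for the exploratory cotinine analysis. Section 14.26 contradicts itself on whom the measure is for, and its assay rule does not supply the data that section 15.4 plans to analyse. Followed as written, the visit-15 comparison and its dichotomous fallback are made in a group selected after randomization by self-reported outcome.

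At the planning rates that group is about 10 and 27 of 98 with honest reporting, or about 14 and 31 with 5% false claims. The contrast within it ranges from none to about a threefold ratio, against 1.25 in all randomized. These sizes rest on the assumed false-claim share, perfect classification by cotinine, no dropout, and the use of continuous-abstinence rates for reported abstinence at visit 15. The selection itself rests on none of these. It follows from the assay rule.

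**What to change.** Reconcile section 14.26 (purpose and assay rule) with the cotinine paragraph of section 15.4. Then choose one of two routes.

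1. *Verification outcome, no additional assays.* Replace the mixed model and its fallback with one binary week-19 outcome in all randomized participants. It is negative only if abstinence is reported and week-19 saliva cotinine is 15 ng/ml or less; a mailed sample is acceptable. It is positive for self-reported smoking, cotinine above 15 ng/ml, a missing sample, or only an early-termination sample. The last condition is needed because section 13.6 runs the visit-15 procedures at early termination, so a negative sample taken on leaving could otherwise count as a week-19 success. Analyse it with the planned logistic regression adjusted for baseline smoking, state the missing-as-positive convention, and report it as exploratory. It overlaps with the planned point-prevalence analysis, but replaces carbon monoxide with cotinine as the check.

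2. *Exposure comparison.* If a continuous or longitudinal comparison is wanted, change the assay rule so that both collected samples are assayed for all subjects in all arms. Collection does not change. The cost is laboratory work: 294 baseline assays plus about 206 (expected completers) to 294 at week 19, so about 500 to 588 in total.

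Route 1 costs only changes of wording in the two sections.

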9 STUDY DESIGN

Two hundred and ninety-four comorbid nicotine-dependent subjects with mild to severe alcohol use disorder who meet eligibility criteria will be randomized to 1 of 3 treatment groups — placebo, low-dose topiramate (up to 125 mg/day), or high-dose topiramate (up to 250 mg/day). Randomization will be achieved using a block randomization procedure in which treatment groups will be stratified to achieve a balance on age of onset for alcoholism (less than 26 years old or 26 years and older), gender, and drinks per drinking day (DDD) (<8 DDD or ≥ 8 DDD) and the number of cigarettes smoked (<20 or ≥ 20 cigarettes/day).

Following randomization, subjects will participate in an 18-week, double-blind treatment period during which they also will receive weekly BBCET, and a self-help manual for smoking cessation. Topiramate and matching placebo will be titrated for the first 5 weeks of the 18-week treatment period. The TQD will be at the beginning of the 6th week of treatment. Subjects will be instructed not to attempt smoking or alcohol cessation prior to the TQD. Setting a TQD at the end of medication titration enables stability of effects, comfort with the medication prior to attempting to cease alcohol and smoking consumption, and an appreciable buildup of medication. However, in cases where individuals either quit smoking or alcohol consumption prior to the TQD, counseling will be directed at helping them maintain their abstinence and reengaging their efforts in the event of relapse. If an individual finds that he or she cannot quit

smoking and/or consuming alcohol completely following the TQD, he or she shall remain in the study and counseling will be directed at the continued setting of reduction goals, with cessation as the ultimate target.

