13.6 Early Termination (ET)

If a subject wishes to withdraw from the study before completing all study visits during the treatment phase then the study staff will schedule an early termination visit. The early termination visit will include all procedures and assessments of visit number 15 (week 19).

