15.4 Subject Populations

The ITT population will be used for the primary analysis and is defined as the subjects who are randomized into the study. The evaluable population is defined as those subjects randomized to the study who completed at least 6 consecutive weeks of maintenance investigational product administration with a dose of at least 50 mg per day for at least 5 days of each 7-day weekly period. The safety population includes all subjects who received at least one dose of investigational product.

Analysis: Data will be summarized with respect to the primary and secondary outcome measures, demographics, and baseline characteristics. In general, quantitative variables will be summarized with standard descriptive statistics (e.g., range, quartiles, means, standard deviations), while frequency tables will summarize categorical variables. Group comparison for quantitative variables will be performed using standard two-sample t-tests or analysis of variance as appropriate. Highly skewed variables may be transformed prior to inferential comparison, or non-parametric methods may be used if needed. Group comparison for categorical variables will be analyzed with two-sample comparisons of proportions, or chi-square tests as appropriate.

The primary efficacy variables will be the PHDD for the drinking outcome and the continuous abstinence rate for the smoking outcome (during the last 4 weeks of treatment, i.e., weeks 15–18 inclusive), respectively. The secondary efficacy variables will be quality of life and measures of alcohol and nicotine craving.

Exploratory outcome variables will include other: 1) measures of drinking severity (i.e., DDD) and abstinence (i.e., percentage of days abstinent; PDA) averaged across either the entire double-blind period or the last 4 weeks of treatment, and 2) smoking measures including the point prevalence abstinence rate and the CO level over either the entire double-blind period or the last 4 weeks of treatment; 3) psychological assessments including measures of nicotine and alcohol withdrawal (WSWS, MOS-Sleep, CIWA-Ar), negative affect (PANAS, CES-D), dependence (FTND), drinking behavior (DrInC) and compliance (BBCET).

The general approach to statistical analyses will be the same as what we utilized in our previous studies.[4, 5] All randomized subjects will be included in the analysis using the intent-to-treat principle. Statistical analyses will be conducted using SAS 9.1 (SAS Institute Inc., Cary, NC).[6]

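### The fallback for non-normal salivary cotinine (a cut at 15 ng/ml, then a generalized linear mixed model) fits neither the two samples collected nor the stated purpose of the measure

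*Combined protocol and SAP*

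**What the plan says.** The exploratory models in section 15.4 give cotinine its own rule: "If the saliva cotinine level satisfactorily achieves criteria for normality as longitudinal data, we will compare the groups using a mixed-effects linear model". If the check fails: "Otherwise, salivary cotinine level will be dichotomized as negative if ≤ 15 ng/ml and positive if > 15 ng/ml", and the binary value is to be "analyzed using the generalized linear mixed models". No random effects are named, and no transformation or rank step comes between the failed check and the cut.

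On sampling, section 13.4 says: "Salivary cotinine level is obtained before randomization and also at visit 15". Table 1 and section 14.26 agree. The early termination visit repeats the visit 15 procedures (section 13.6), so it stands in for that sample and adds no third time point.

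On purpose, section 14.26 says: "Salivary cotinine level will be used as an additional objective measure of tobacco exposure for those who are still smoking". It presents 15 ng/ml as the level that separates non-smokers from smokers. It also has the laboratory assay only the samples of subjects who report abstinence.

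For skewed variables in general, section 15.4 says: "Highly skewed variables may be transformed prior to inferential comparison, or non-parametric methods may be used if needed". For subjects who cannot quit, section 9 says: "counseling will be directed at the continued setting of reduction goals, with cessation as the ultimate target".

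**The concern.** The fallback is the likely route. At the end of treatment the values would mix quitters near zero with continuing smokers well above the cut, so a normality check would probably fail. Two things then look wrong.

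- **The model.** A mixed model for a binary outcome learns about between-subject variance from repeated, varying values within subjects. Here there are two values, and one is expected to be positive for nearly everyone.
- **The scale.** A threshold that separates smokers from non-smokers cannot grade exposure among smokers. Any effect of either dose on exposure in those who keep smoking would be almost invisible, and the binary result would largely repeat the abstinence outcome.

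What is at stake is an exploratory analysis: a reported odds ratio that depends on an arbitrary variance, and the loss of an objective measure of smoking reduction.

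**Working it through.** **1. The plan's own figure.** Section 15.5 uses abstinence of 10% vs 28%, alpha 0.017 and power 0.80. Two-sided, without continuity correction:

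n = [z(α/2)·√(2p̄q̄) + z(β)·√(p₁q₁ + p₂q₂)]² / (p₁ − p₂)²

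With p̄ = 0.19 this is [2.387 × 0.5548 + 0.8416 × 0.5400]² / 0.18² = 97.7, so 98 per arm, as stated (power 0.802). The plan gives no power for cotinine. The steps below borrow its 98 per arm and its rates.

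**2. How many informative time points.** Section 10.1 requires an average of at least 5 cigarettes/day, with expired CO ≥ 10 ppm or urinary cotinine ≥ 3. Baseline saliva should therefore exceed 15 ng/ml for practically all subjects. This is inferred from CO and urine; saliva is not an entry test. It leaves visit 15 as the one informative binary value.

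**3. What a random-intercept logistic model can estimate.** Take 98 × 0.10 ≈ 10 and 98 × 0.28 ≈ 27 subjects negative at visit 15. The ordinary odds ratio is (27 × 88)/(71 × 10) = 3.35. The maximized log-likelihood is 10·ln(10/98) + 88·ln(88/98) + 27·ln(27/98) + 71·ln(71/98) = −89.98. Fixing the random-intercept SD and refitting by quadrature gives:

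| Random-intercept SD | Log-likelihood | Subject-specific odds ratio |
|---|---|---|
| 0 | −89.984 | 3.35 |
| 0.5 | −89.984 | 3.50 |
| 1 | −89.984 | 3.97 |
| 2 | −89.984 | 6.11 |
| 3 | −89.984 | 10.57 |
| 5 | −89.984 | 35.97 |

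An all-positive baseline does not help. The fit improves as the baseline intercept grows, and at an intercept of 20 the log-likelihood is again −89.984 for SDs of 0, 1, 2 and 3. The data cannot choose among these odds ratios. The visit 15 proportions and the ordinary odds ratio are the same throughout.

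**4. What the cut discards among continuing smokers.** The documents give no cotinine level or SD. Assume a geometric mean of 100–300 ng/ml, log-SD 0.6–1.0, 98 × 0.90 ≈ 88 continuing smokers per arm, and two-sided alpha 0.05/3 (borrowed from the primary power calculations). For a 35% fall with no extra quitting, at 200 ng/ml and log-SD 0.8:

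- Log scale: |ln 0.65| = 0.431 and SE = 0.8·√(2/88) = 0.121, giving power 0.88.
- Cut: the proportion above 15 ng/ml moves from 0.9994 to 0.9965, giving power 0.02.

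Over the whole range, power is 0.68–0.99 on the log scale and 0.01–0.13 for the cut. This shows the information lost. It is not a proposed analysis, because continuing smokers are selected after randomization.

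**5. All-subject analyses.** Simulation of 2000 replicates per scenario with 98 per arm and alpha 0.05/3. Assumed: smokers around 200 ng/ml, quitters around 2, log-SD 0.8, baseline correlation 0.6, floor 1 ng/ml, every sample assayed.

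| Abstinence; fall in smokers | Cut at 15 | Log ANCOVA | Rank ANCOVA |
|---|---|---|---|
| 10% vs 28%; 0% | 0.821 | 0.765 | 0.505 |
| 10% vs 28%; 20% | 0.822 | 0.915 | 0.904 |
| 10% vs 28%; 30% | 0.810 | 0.960 | 0.984 |
| 10% vs 28%; 40% | 0.818 | 0.988 | 0.999 |
| 10% vs 10%; 30% | 0.016 | 0.187 | 0.634 |

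Independent reruns of the last row gave about 0.20 for log ANCOVA and 0.65 for rank ANCOVA. Over log-SD 0.6–1.0 and smoker levels of 100–300 ng/ml, log ANCOVA in that scenario has 0.15–0.30. With 28% abstinent in both arms and a 30% fall, log ANCOVA has 0.07 and rank ANCOVA 0.24.

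**The case against.** - **The comparison can be estimated.** A reader might infer that the fallback cannot estimate a treatment effect, or that it will fail to converge. The documents do not support either. Only the random-effect variance and the subject-specific odds ratio lack support. Section 15.4 names no random effects and does not say that baseline is modelled as a response; with one usable time point the analysis can reduce to logistic regression. Non-convergence has not been demonstrated. A few baseline values at or below 15 ng/ml would also give weak identification. This stands.
- **Smokers may have no value at all.** It is tempting to say that every continuing smoker gets the same value. Under section 14.26's assay rule, acknowledged smokers would have no value on any scale, so changing the model alone recovers nothing for them. This stands, and it makes reconciling that section a precondition.
- **The full-scale alternative is imperfect.** All-subject log ANCOVA has power 0.765 with no reduction among smokers, so a positive result may be quitting alone. It is weak when only exposure falls. This stands and limits what the fix can claim.
- **Reduction is covered elsewhere.** Section 15.4 models cigarettes per smoking day and lists CO level as an exploratory outcome. Its general sentence on skewed variables could be read as allowing a transformation before the normality check. This lowers the importance, but the cotinine rule itself names no such step.

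**Conclusion.** The fallback is poorly matched to the data and to the purpose of the measure. If a subject random effect is fitted, the subject-specific odds ratio is essentially arbitrary (3.35 to about 36 at the same likelihood, for 27/98 vs 10/98). This rests on the inference that baseline saliva is positive for practically everyone. The visit 15 comparison between arms is sound by ordinary logistic regression.

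The cut also hides exposure differences among continuing smokers, who are 72–90% of an arm at the planning rates (1 − 0.28 to 1 − 0.10). That loss becomes the operative one only if their samples are assayed. All power figures for cotinine rest on assumed levels, spreads and correlations that the documents do not give.

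The point is minor. The cotinine model is exploratory and bears on neither the primary conclusions nor the sample size.

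**What to change.** 1. In section 15.4, replace the mixed model for the binary value with ordinary logistic regression of 15 ng/ml status at visit 15 on treatment arm. This is SAP wording with no real downside.
2. In section 14.26, reconcile the stated purpose (subjects still smoking) with the assay rule (only those who report abstinence), and say which baseline and visit 15 samples are assayed.
3. Once that is settled, also analyse visit 15 cotinine on its full scale without a normality gate, adjusted for pre-randomization cotinine. Report log ANCOVA (values below the assay limit set to that limit) and rank ANCOVA side by side as named analyses. State that an all-subject result mixes quitting with reduction.

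The cost is SAP wording plus assays of saliva that the plan already collects from all subjects. Under the assumptions above, if the drug affects quitting only, power against the cut falls by about 5 points for log ANCOVA (0.821 − 0.765 = 0.056) and about 32 for rank ANCOVA (0.821 − 0.505 = 0.316). If only exposure falls (30%, with 10% abstinent in both arms), power is about 0.20 for log ANCOVA and 0.65 for rank ANCOVA. Neither method is better in every case, which is why both should be named and the 15 ng/ml comparison kept beside them.
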